6.9.2. Oral Dosing

The Month 1 Visit during the Oral Lead-in Phase for participants randomized to CAB + RPV but choosing to participate in the oral lead in is expected to occur 4 weeks (± 3 days) after the Day 1 visit. Visits for participants on the BIK arm are expected to occur every 56 days as projected according to the Day 1 visit. There is a ± 3 -day visit window, from the projected visit date (Maintenance Phase of the study). However, the number of tablets dispensed should be considered when scheduling the next visit.

Any interruption in therapy (scheduling conflicts, life circumstances, *etc.*) during any oral dosing period that is greater than 7 consecutive days must be discussed with the Medical Monitor prior to resumption of therapy. The Medical Monitor must be contacted upon site staff becoming aware of resumption in therapy, if therapy was resumed without prior approval.

Visits for participants in the Long Term Follow Up are expected to occur as projected according to the last injection. There is no calendar defined visit window in the Long Term Follow Up Phase. In general, four LTFU visits should occur from the last date of LA therapy until week 52 with clinic visits at months 3, 6, 9 and 12, although the timing of the actual visits are flexible, but not the frequency, in LTFU.

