3. OBJECTIVES AND ENDPOINTS

Objectives	Endpoints
Primary	
To demonstrate the non-inferior antiviral activity of CAB LA + RPV LA every two months compared to a BIK single tablet regimen administered once daily over 12 months in suppressed HIV-1 infected antiretroviral therapy (ART)-experienced participants	Proportion of participants with plasma HIV-RNA greater than or equal to 50 copies/mL as per Food and Drug Administration (FDA) Snapshot algorithm at Month 12 (OLI and BIK)/Month 11 (D2I) (Intent-to-Treat Exposed [ITT-E] population)
Secondary	
To demonstrate the antiviral and immunologic response with the use of CAB LA + RPV LA every 2 months compared to a BIK single tablet regimen administered once daily	Proportion of participants with plasma HIV-1 RNA <50 c/mL (c/mL) at Month 6 and Month 12 (OLI and BIK)/Month 5 and Month 11 (D2I) using the FDA Snapshot algorithm (Intent-to-Treat Exposed [ITT-E] population)

Objectives	Endpoints
	
Proportion of participants with protocol-defined confirmed virologic failure (CVF) through Month 6 and Month 12 (OLI and BIK)/Month 5 and Month 11 (D2I).
 
Proportion of participants with HIV-RNA greater than or equal to 50 c/mL as per FDA Snapshot algorithm at Month 6, and Month 12 (OLI and BIK)/Month 5 and Month 11 (D2I)
 
Absolute values and changes from Baseline in viral load and CD4+ cell count over time including Month 6 and Month 12 (OLI and BIK)/Month 5 and Month 11 (D2I)

To assess viral resistance in participants experiencing protocol-defined confirmed virologic failure	Incidence of treatment emergent genotypic and phenotypic resistance to CAB, RPV, BIC, FTC, and TAF through Month 6 and Month 12 (OLI and BIK)/Month 5 and Month 11 (D2I).
To evaluate renal (in urine and blood) and bone (in blood) biomarkers in participants treated with CAB LA + RPV LA compared to BIK	Change from Baseline (Day 1) in renal and bone biomarkers at Months 6 and 12 (OLI and BIK)/Month 5 and Month 11 (D2I).
To evaluate Metabolic Syndrome for participants treated with CAB + RPV and BIK	Change from Baseline in proportions of participants with Metabolic syndrome at Months 6 and 12 (OLI and BIK)/Month 5 and Month 11 (D2I)
To evaluate insulin resistance in participants treated with CAB LA + RPV LA compared to BIK	Change from Baseline (Day 1) in homeostasis model of assessment-insulin resistance (HOMA-IR) at Months 6 and 12 (OLI and BIK)/Month 5 and Month 11 (D2I).

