Continue on current ART (BIK) regimen for 12 months. Participants who successfully complete Month 12 (without meeting study defined withdrawal criteria and who remain virologically suppressed (HIV-1 RNA <50 c/mL) will be given the option to switch to the LA arm in the Extension Phase (with or without an OLI) or to successfully complete and withdraw from the study (no withdrawal visit needed).

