6.9.1. IM Dosing

Participants receiving CAB LA and/or RPV LA are anticipated to be at risk for development of virologic resistance if ART is interrupted. The time period during which participants are at risk for development of virologic resistance may be determined by the period between when drug levels fall below therapeutic values and when they fall below levels which exert selective pressure on HIV. This time period will vary by ART agent and is dependent upon effective concentration, inhibitory concentration, and half-life. Plasma concentrations of both LA drugs may be measurable for more than one year following IM injections. Any interruption in IM dosing should be discussed with the Medical Monitor. Investigators should ensure that the participant initiates alternative highly active ART to minimize the risk of developing resistance as concentrations of CAB and RPV decline over time.

IM dosing is expected to occur during the week in which the participant's projected visit falls (as according to the date of the first injection). The first injections for participants who choose to start injections immediately will occur at Day 1. The first injections for participants electing to participate in the oral lead are administered at Month 1 (can be performed before lab results become available), and the second injections are given at Month 2.

The participant's projected visit is determined by their first injection date and, ideally, is the same date for every injection. For example, if the 1st dose (Month 1) is January 15th, then dose 2 (Month 2) will be February 15th, and dose 3 (Month 4) will be April 15th, etc.

Since the first injection visit (Day 1 or Month 1) will determine the future injection visit schedule for participants, planning for the first injection visit date (within allowed visit windows) should take into consideration the availability of the participants to adhere to future visit windows (planned vacations, business trips, weekends, holidays, *etc.*).

Dosing for participants randomized to CAB LA + RPV LA is as follows:

All injections should be planned as single injections per drug.

6.9.1.1. IM injections every 2 months (Oral Lead In):

Month 1 – CAB LA 600 mg + RPV LA 900 mg IM, each given as 1 X 3 mL IM injection

Month 2 - CAB LA 600 mg + RPV LA 900 mg IM, each given as 1 X 3 mL IM injection

Month 4 and Q2M thereafter - CAB LA 600 mg + RPV LA 900 mg IM, every 2 months until Month 12, each given as 1 X 3 mL IM injection

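### BIK Month 12 falls 336 days after Day 1, about 11 calendar months: it carries the oral lead-in label but the direct-to-injection timing, and lead-in participants are followed about 27 days longer

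*Protocol*

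**What the plan says.** Section 6.9.2 fixes the BIK clock: "Visits for participants on the BIK arm are expected to occur every 56 days as projected according to the Day 1 visit", with a window of ±3 days. Footnote b to the Schedule of Activities (Section 1.3) repeats this. The BIK visits are labelled Months 2, 4, 6, 8, 10 and 12. Section 4.1.2 describes the arm as "Continue on current ART (BIK) regimen for 12 months", and the Synopsis and Section 4.1 also give 12 months.

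The long-acting (LA) arm runs on a different clock. Under Section 6.9.1, "The participant's projected visit is determined by their first injection date and, ideally, is the same date for every injection". The example there starts on 15 January, "then dose 2 (Month 2) will be February 15th, and dose 3 (Month 4) will be April 15th". Section 4.4.1.2 separates dosing every 8 weeks (7 doses in year 1) from dosing every 2 months (6.5 doses), so an LA month cannot be read as 28 days. For OLI participants the Month 1 visit, which is the first injection, "is expected to occur 4 weeks" after Day 1, ±3 days (Section 6.9.2). D2I participants have their first injection on Day 1.

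The primary endpoint in Section 3 is read at "Month 12 (OLI and BIK)/Month 11 (D2I) (Intent-to-Treat Exposed [ITT-E] population"). Section 9.4.1 uses the same pairing, and Section 9.5 sets the interim analysis at Month 6 (OLI and BIK) and Month 5 (D2I).

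**The concern.** A BIK month is 28 days and an LA month is a calendar month, and the protocol nowhere says that this is intended. The one-month label difference between OLI and D2I is declared. The difference in what a month means between BIK and the injection arm is not.

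Two things follow. First, the schedule given to sites does not deliver the 12-month BIK period that the protocol describes. Second, the labels suggest that BIK and OLI are compared at equal follow-up, and at the primary visit they are not. This matters most for outcomes that accumulate over time and are reported through Month 5/6 and Month 11/12: adverse events, discontinuations due to adverse events, and confirmed virologic failure. Change-from-baseline endpoints at those visits (renal and bone biomarkers, HOMA-IR, metabolic syndrome, treatment satisfaction) are also read at somewhat different times.

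**Working it through.** All days are elapsed days after Day 1.

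**Inputs.** BIK interval 56 days, window ±3, and OLI Month 1 at 28 days, ±3 (Section 6.9.2). Injection visits on calendar months from the first injection, window ±7 from the third injection on (Section 6.9.1). Mean calendar month 365.25/12 = 30.44 days.

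**The stated figure first.** Twelve months is 12 × 30.44 = 365 days. The BIK schedule gives 6 × 56 = 336 days, and 336/30.44 = 11.04 months. The stated 12 months is not reproduced; the schedule falls 29 days short.

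**Timing by visit label L.** BIK: 28 × L. OLI: 28 + (L − 1) × 30.44. D2I, whose label is one lower: (L − 1) × 30.44.

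| Label (BIK and OLI / D2I) | BIK | OLI | D2I | OLI − BIK | D2I − BIK |
|---|---|---|---|---|---|
| 2 / 1 | 56 | 58 | 30 | +2 | −26 |
| 4 / 3 | 112 | 119 | 91 | +7 | −21 |
| 6 / 5 | 168 | 180 | 152 | +12 | −16 |
| 8 / 7 | 224 | 241 | 213 | +17 | −11 |
| 10 / 9 | 280 | 302 | 274 | +22 | −6 |
| 12 / 11 | 336 | 363 | 335 | +27 | −1 |

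With real dates (starts on the 15th of every month, 2020 to 2024), OLI Month 12 falls on days 362 to 365 and D2I Month 11 on days 334 to 337.

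**Can the windows close the gap?** The latest in-window BIK Month 12 visit is 336 + 3 = day 339. The earliest in-window OLI Month 12 visit is 362 − 3 − 7 = day 352. They do not meet.

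**Extra follow-up, OLI over BIK, at the primary visit.** 27/336 = 8.0%.

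**Pooled LA arm.** Let f be the share choosing OLI, which the protocol does not give. The pooled mean gap to BIK is 28f − 1 days at the primary visit: −1 at f = 0, +13 at f = 0.5, +27 at f = 1. At Month 5/6 it is 28f − 16 days: −16, −2 and +12.

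**Effect on the primary endpoint.** Assume failures accrue at a constant rate reaching 2% in 336 days. The extra OLI time then adds 2% × 27/336 = 0.16 points. Seen from the other side, if BIK's assumed 1% applied at day 363 and accrued linearly, day 336 would give 1% × 336/363 = 0.93%, a shift of 0.07 points. The stated 85% power reproduces with the named score test: exact enumeration at 436 and 218, 2% against 1%, margin 4%, gives 85.1%. With BIK at 0.93% it becomes 83.9%.

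**The case against.** There are several fair points in favour of the plan.

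- The OLI/D2I offset is declared throughout and aligns both LA routes at 11 months after the first injection. This stands. The 28-day spread at Month 5/6 (180 − 152) lies within one randomized arm and is not a contrast between arms.
- The choice of route comes after randomization, but the ITT-E population (Section 9.3.1) is analysed by randomized treatment, so both routes stay in the LA arm. This stands for the primary comparison.
- The 56-day interval has a practical reason. Section 6.9.2 asks sites to take account of the tablets dispensed, and bottles hold 30 (Section 6.1.2). If two are given per visit, which is an assumption, 60 tablets cover 59 days but not a calendar interval of 61 or 62. Table 8 also places Week 48 study-report data under a Month 12 heading. These are reasons to keep the interval, but they do not make 336 days equal 12 months.
- Analysis windows may be in the SAP, which is not at hand. Section 7.1.7.1 shows that they exist, because a retest within 4 weeks must fall in the same window. So a claim that Snapshot windows sit off-centre for some groups is not supported.

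A reader might also infer that the three groups are at different times at every nominal visit. The table shows otherwise: BIK and D2I coincide at the primary visit, and OLI and BIK are 2 days apart at Month 2. Nor do the documents support a threat to the primary conclusion. At that visit the extra time is on the LA arm, which works against claiming non-inferiority, and a Snapshot result depends largely on the viral load in the visit window rather than on accumulated time.

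**Conclusion.** The point holds as a contradiction over what a month means, with a modest analytical consequence. Followed as written, the protocol gives BIK 336 days (±3) to Month 12, not 12 months, and reads OLI about 27 days later under the same label. At Month 5/6 the LA routes lie about 16 days before and 12 days after BIK.

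The day counts rest only on protocol text and calendar arithmetic. The size of the effect rests on assumptions: a constant failure rate for the 0.16 points, which is a ceiling that applies to OLI participants alone, and an unknown OLI/D2I split for the pooled gap of −1 to +27 days at the primary visit. Against a 4-point margin the primary result is not at risk. The correction is worth making because it is cheap, because the cumulative safety and failure summaries use unequal follow-up, and because an SAP cannot correct a visit interval and a duration that disagree in the protocol.

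**What to change.** Reconcile Section 1.3 (footnote b) and Sections 4.1.2, 6.9.1, 6.9.2 and 9.4.1 on what a month means in each arm:

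- Keep the 56-day BIK visits. State that BIK Month 6 and Month 12 mean Week 24 (168 days after Day 1) and Week 48 (336 days).
- Correct the 12-month description of the BIK period in the Synopsis and in Sections 4.1 and 4.1.2 so that it agrees with that schedule.
- Compare cumulative adverse event, discontinuation and confirmed virologic failure rates up to a common study day from Day 1 in both arms, for example day 336 for Month 11/12. The exact day, and the Snapshot windows, can be left to the SAP.

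BIK visits should not be moved to calendar months. Month 12 would then be at about day 365, close to OLI but 365 − 335 = 30 days after D2I. No single BIK schedule matches both routes.

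The cost is wording and one analysis rule, with no added visits. A few late OLI events fall outside the common cut-off. For confirmed virologic failure, which is detected at visits, OLI's last scheduled viral load before day 336 is Month 10 at about day 302, so the planned by-visit summary should stay beside the common-day one.

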6.10. Treatment after the End of the Study

The investigator is responsible for ensuring that consideration has been given to the post-study care of the participant's medical condition, whether or not ViiV/GSK is providing specific post-study treatment. Participants randomized to CAB LA + RPV LA arm, who have successfully completed 12 months of treatment will continue to have access to both CAB LA and RPV LA in the Extension Phase until study treatment is either locally approved and commercially available, the participant no longer derives clinical benefit, the participant meets a protocol-defined reason for discontinuation or until development of either CAB LA or RPV LA is terminated. Participants randomized to the BIK arm who have successfully completed 12 months of treatment will be given the option of continuing onto the Extension Phase to receive CAB LA + RPV LA. If these participants choose not to continue, they will end participation in the study after Month 12 will be responsible for obtaining post-study treatment.

6.11. Concomitant Therapy

Participants should be advised to notify their investigator of any current or proposed concomitant medication, whether prescribed or over-the-counter, because of the potential drug:drug interactions between such treatments and the study drugs. The investigator should evaluate any potential drug:drug interactions at every visit, including reviewing the most current version of the investigator brochures, the U.S and/or local prescribing information for RPV and BIK, especially if any new concomitant medications are reported by participants. All concomitant medications, blood products, and vaccines taken during the study will be recorded in the eCRF. The minimum requirement is that the drug name, route, and the dates of administration are to be recorded.

Concomitant medications (prescription and non-prescription) should be administered only as medically necessary during the study (except prohibited medications described in Section 6.11.1). Chemoprophylaxis for HIV-associated conditions is encouraged, if appropriate, at the discretion of the participant and their physician.

Because non-HIV vaccines may cause a temporary increase in the level of plasma HIV-1 RNA, it is highly recommended that a vaccine, if necessary, be given during or immediately after a scheduled visit after all laboratory tests have been drawn. This approach will minimize the risk of non-specific increases in the level of plasma HIV-1 RNA at the next scheduled assessment.

Other IM injectables (with exceptions below) are permitted but must be administered away from the site of IP administration if possible (should be spaced 2 cm or more away from site of IP injection).

Hepatitis C infection treatment is allowed throughout the entire study. If HCV treatment occurs during the study, a DHHS approved HCV regimen should be used to limit any drug-drug interactions that may occur. Options for treatment of HCV should be discussed with the Medical Monitor prior to initiation of therapy.

Antacid and H2 Antagonist Use:

While both oral CAB and RPV have dosing requirements with antacid products containing divalent cations, only oral RPV has requirements for dosing with H2 antagonists. Since co-administration of oral CAB and RPV is required in this study, the most restrictive dosing requirements must be taken into consideration.

CAB oral administration only: Antacid products containing divalent cations (e.g., aluminium, calcium, and magnesium) must be taken at least 2 hours before or at least 4 hours after CAB.

Concurrent administration of multivitamins is acceptable.

Oral RPV administration only:

- Antacid products containing divalent cations (e.g., aluminium, calcium, and magnesium) must be taken at least 2 hours before or at least 4 hours after RPV.
- H2-Receptor antagonists (e.g. cimetidine, famotidine, nizatidine, ranitidine) may cause significant decreases in RPV plasma concentrations. H2-antagonists must be taken at least 12 hours before or at least 4 hours after taking RPV.
- RPV should not be co-administered with proton pump inhibitors, such as esomeprazole, lansoprazole, omeprazole, pantoprazole, rabeprazole.

Administration of clarithromycin, erythromycin and telithromycin is not recommended with RPV due to possible increase in plasma concentration of RPV due to CYP3A enzyme inhibition. Where possible, alternatives such as azithromycin should be considered.

Drugs that cause Torsade de Pointes (TdP) should be used with caution when taking rilpivirine (see SPM for list of drugs associated with TdP).

BIK: BIK and calcium-containing supplements can be taken together, without regard to food.

BIK should be administered at least 2 hours before iron supplements or taken together with food.

BIK should not be taken simultaneously with supplements containing magnesium and/or aluminium due to the expected substantial decrease of BIC exposure.

BIK should be administered at least 2 hours before, or with food 2 hours after antacids containing magnesium and/or aluminium.

Metformin concentrations may be increased by BIK. Refer to the prescribing information of metformin for assessing the benefit and risk of concomitant use of BIK and metformin.

Clinical monitoring is recommended for participants taking methadone as methadone maintenance therapy may need to be adjusted in some participants.

Approved hormonal contraception may be administered. However, the investigator should consult local prescribing information for guidance on the use of hormonal contraceptives with background ART as some antiretrovirals have clinically significant drug interactions with these products.

Please refer to the local prescribing information for other drugs that should be used with caution, require dose adjustment, or increased clinical monitoring if taken with BIK.

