6. STUDY INTERVENTION

The term ‘study treatment’ is used throughout the protocol to describe any combination of products received by the participant as per the protocol design. **Study treatment is defined as any investigational treatment(s), marketed product(s), placebo, or medical device(s) intended to be administered to a study participant according to the study protocol.** Study treatment may therefore refer to the individual study treatments or the combination of those study treatments.

In this study, investigational product (IP) refers to oral BIK single tablet regimen (or alternately BIK), oral CAB, and CAB LA, which will be supplied by GlaxoSmithKline and oral RPV and RPV LA which will be supplied by Janssen Pharmaceuticals.

Participants entering the Long-Term Follow-Up Phase will not have their selected HAART provided as clinical trial material. The selected HAART will be recorded on the Concomitant Antiretroviral Therapy (ConART) eCRF page.

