In addition, participants must discontinue the following (or change to an allowable alternative) while receiving treatment with RPV:

- Oral RPV: proton pump inhibitors, such as esomeprazole, lansoprazole, omeprazole, pantoprazole, rabeprazole;
- Both Oral and RPV LA: systemic dexamethasone (more than a single dose).

If the participant cannot discontinue use or change to an allowable alternative while receiving treatment with RPV, the participant should not be randomized into the study.

Please refer to the current RPV Investigator brochure and local prescribing information for other drugs that are prohibited, should be used with caution, require dose adjustment, or increased clinical monitoring if taken with oral RPV.

Concurrent with either CAB LA or RPV LA

In addition, for participants receiving CAB LA and RPV LA, use of anticoagulation agents for greater than 14 days is prohibited, with the exception of the use of anticoagulation for DVT prophylaxis (e.g., postoperative DVT prophylaxis) or the use of low dose aspirin (daily doses ≤ 325 mg). Systemic anticoagulation (including prophylaxis doses) on the day of an IM injection should be avoided.

Concurrent with BIK

The following medications or their equivalents may cause decreased concentrations of BIC. Therefore, the following medications must not be administered concurrently with BIC:

- Carbamazepine
- Oxcarbazepine
- Phenobarbital
- Phenytoin
- Rifampicin / Rifampin
- Rifabutin
- Rifapentine
- St. John's wort (*Hypericum perforatum*)

- Dofetilide is prohibited as BIC may inhibit renal tubular secretion resulting in increased dofetilide/pilsicainide concentrations and potential for toxicity.

Note: Any prohibited medication that decrease BIC concentrations should be discontinued for a minimum of four weeks or a minimum of three half-lives (whichever is longer) prior to the first dose. Any other prohibited medication should be discontinued for a minimum of two weeks or a minimum of three half-lives (whichever is longer) prior to the first dose.

Please refer to the current local prescribing information for other drugs that should be used with caution, require dose adjustment, or increased clinical monitoring if taken with BIK.

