7.1.4. QTc Stopping Criteria

A participant who has a QTc interval >550 msec considered causally related to IP will be withdrawn from the study. The QTc should be based on averaged QTc values of triplicate electrocardiograms obtained over a brief (e.g., 5 to 10 minute) recording period.

If an alternative cause of the QT prolongation is determined (e.g., participant receiving drug known to cause prolonged QT or TdP), the IP may be restarted (or continued) after consultation and agreement with the Medical Monitor. RPV and RPV LA should not be administered to patients who are receiving a drug known to be associated with TdP.

When performing ECGs, the *same* QT correction formula *must* be used for *each individual participant* to determine eligibility for, and discontinuation from, the study. This formula may not be changed or substituted once the participant has been enrolled.

For example, if a participant is eligible for the protocol based on QTcB, then QTcB must be used for discontinuation of this individual participant as well.

Once the QT correction formula has been chosen for a participant's eligibility, the *same formula* must continue to be used for that participant *for all QTc data being collected for data analysis*. Safety ECGs and other non-protocol specified ECGs are an exception.

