8.2.5. Electrocardiograms

A 12-lead ECG will be performed in a semi-supine position. On Day 1, (Baseline), ECGs should be performed in triplicate prior to first dose. At Day 1, Month 1 (OLI) and Month 12 (OLI)/Month 11 (D2I) of the Maintenance Phase, a 2-hour post dose ECG will be performed for participants receiving CAB LA + RPV LA with an allowable window of ± 30 minutes. An ECG machine that automatically calculates the heart rate and measures PR, QRS, QT, and QTc intervals is preferred, and these calculated numbers can be used for reporting purposes. Otherwise, an appropriately qualified ECG reader must interpret the results. The same interpreter should assess all ECGs for each participant. Regardless, each ECG should be reviewed by a qualified ECG reader. The qualified ECG reader will make the non-calculated ECG interpretations. Refer to the SoA for collection timepoints (Section 1.3). Refer to Section 7.1.4 for [QTc] withdrawal criteria and additional [QTc] readings that may be necessary.

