8.3.11.5. QTc Prolongation

Participants with an average QTc interval > 550 msec from three or more tracings separated by at least 5 minutes should have IP discontinued. These criteria are based on an average QTc value of triplicate ECGs. If an ECG demonstrates a prolonged QT interval, obtain 2 more ECGs over a brief period (~5-10 minutes) and use the averaged QTc values of the 3 ECGs to determine whether the participant should be discontinued from the study. If an alternative cause of the QT prolongation is determined (e.g.,

participant receiving drug known to cause prolonged QT or TdP), then IP may be restarted after consultation with, and agreement by, the Medical Monitor.

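### After QTc above 550 msec with a Torsade-associated drug as the alternative cause, Section 7.1.4 bars rilpivirine while that drug is being taken; Section 8.3.11.5 omits the bar, and the scope of the bar against the caution rule in Section 6.11 is not stated

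*Protocol*

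**What the plan says.** Four parts of the protocol bear on a TdP-associated drug taken with rilpivirine (RPV).

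- **Section 5.2, exclusion 36** makes use of such drugs exclusionary and refers to a list in the Study Procedures Manual (SPM).
- **Section 6.11**, on co-medication during the study, says: "Drugs that cause Torsade de Pointes (TdP) should be used with caution when taking rilpivirine". It refers to an SPM list as well.
- **Section 7.1.4** covers QTc above 550 msec. If another cause is found, with a QT- or TdP-prolonging drug as the example, "the IP may be restarted (or continued) after consultation and agreement with the Medical Monitor". The next sentence says: "RPV and RPV LA should not be administered to patients who are receiving a drug known to be associated with TdP".
- **Section 8.3.11.5** covers the same threshold and the same example: "participant receiving drug known to cause prolonged QT or TdP), then IP may be restarted after consultation with, and agreement by, the Medical Monitor". It has no sentence on withholding RPV.

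The Section 6 definition of investigational product (IP) includes "oral RPV and RPV LA which will be supplied by Janssen Pharmaceuticals", alongside cabotegravir (CAB) and BIK. Section 8.2.5 tells ECG readers: "Refer to Section 7.1.4 for [QTc] withdrawal criteria". Section 8.3.11.5 has no such pointer. The part of Section 6.11.1 on drugs taken with RPV names proton pump inhibitors for oral RPV and, for both formulations, only "Both Oral and RPV LA: systemic dexamethasone (more than a single dose"). It does not mention TdP drugs.

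**The concern.** Section 6.11 also says: "The investigator should evaluate any potential drug:drug interactions at every visit". A TdP drug newly prescribed to a participant on RPV is therefore something sites will be looking for, and the protocol should give them one answer. There are two situations.

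- **Before any QT prolongation.** Section 6.11 allows co-administration with caution. Section 7.1.4, taken at its general wording, says RPV should not be given.
- **After QTc above 550 msec attributed to a TdP drug.** A site reading Section 7.1.4 is told not to give RPV while that drug is being taken. A site reading Section 8.3.11.5 sees only that IP may be restarted with Medical Monitor agreement. It could ask to restart RPV with the other drug still on board.

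The second situation matters more, because the participant has already shown marked prolongation. Timing matters too. Section 6.9.1 says concentrations of both long-acting drugs may be measurable for more than a year after injection, so the rule needs to be clear before the next dose.

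**Working it through.** No plan figure needs reproducing. The check sets the texts side by side.

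| Section | Situation | RPV with a TdP drug |
|---|---|---|
| 5.2, exclusion 36 | Entry | Participant excluded |
| 6.11 | Co-medication on study | Allowed with caution; no Medical Monitor step in that sentence |
| 6.11.1 | Prohibited list | TdP drugs not listed |
| 7.1.4 | QTc above 550 msec, alternative cause | IP may be restarted or continued with agreement; RPV should not be given while the drug is taken |
| 8.3.11.5 | Same event | IP may be restarted with agreement; silent on RPV |

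**Step 1: Sections 7.1.4 and 8.3.11.5.** Threshold, example and Medical Monitor requirement are the same. They differ in the sentence on RPV, which only Section 7.1.4 has. Because IP includes both RPV formulations, the restart permission in Section 8.3.11.5 on its face reaches RPV.

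**Step 2: within Section 7.1.4.** IP also covers CAB and BIK, so a general restart permission followed by a limit on RPV can be read as a rule and its exception. For a CAB + RPV participant, Section 6.9 requires all antiretrovirals to be held if one is held for toxicity or an adverse event. The two sentences then fit together only if the TdP drug is stopped first. Section 7.1.4 leaves that to inference and Section 8.3.11.5 does not say it.

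**Step 3: Sections 7.1.4 and 6.11.** The sentence in Section 7.1.4 sits under the QTc stopping criteria but refers to patients receiving such a drug, without limiting itself to those who crossed the threshold. Read generally, it conflicts with Section 6.11. Read as applying only after prolongation, it does not. The protocol does not say which is meant.

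**Step 4: does another section settle it?** Exclusion 36 governs entry. The Month 13 eligibility check may apply it again to BIK participants who switch. Neither governs a drug started once RPV is under way. Section 6.11.1 has no TdP entry, which fits caution better than a general bar. Its pointer to the RPV brochure and local prescribing information concerns oral RPV.

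**Step 5: population governed.** From the 2:1 allocation of 654 in Section 9.2.1:

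- CAB LA + RPV LA: 654 × 2/3 = 436
- BIK: 654 − 436 = 218, who may switch in the Extension Phase

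Both agree with the 85% power row of Table 7. They count the people the wording covers, not the people affected.

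**The case against.** The strongest reply is that this is drafting, not contradiction. Section 8.3.11.5 is silent on RPV with a TdP drug; it does not approve the combination. Section 8.2.5 names Section 7.1.4 as the place for QTc withdrawal criteria. Every such restart needs Medical Monitor agreement under either section, so no site may act on Section 8.3.11.5 alone. The bar follows directly on the post-prolongation rule and may be meant only for that setting, with Section 6.11 governing routine co-medication. Exclusion 36 already removes TdP drugs at entry.

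Much of this stands. A reader might infer that the protocol holds three competing rules. It does not: Section 8.3.11.5 is an incomplete restatement of Section 7.1.4, not a third rule. A reader might also infer that a general prohibition was intended and that the caution sentence in Section 6.11 is simply wrong. The documents do not establish that. The absence of TdP drugs from Section 6.11.1 points the other way, and the SPM list that would show the practical reach of a bar is not at hand.

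Two things survive the reply. The two restart sections still differ for the same event, and Medical Monitor agreement does not cure that, because the Monitor works from the same text. And the scope of the Section 7.1.4 sentence has to be guessed.

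**Conclusion.** The point holds in limited form and should be corrected. For QTc above 550 msec with a QT or TdP drug as the alternative cause, Section 8.3.11.5 omits a restriction that Section 7.1.4 imposes, and as written it could lead to RPV being restarted with that drug still being taken. Separately, Sections 6.11 and 7.1.4 conflict if the latter is read at its general wording; that part depends on a scope the protocol leaves open.

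The wording covers 436 planned participants, plus up to 218 who may switch. Given exclusion 36, the practical exposure is to TdP drugs started on study. How many participants that will be is not stated and cannot be estimated from the protocol. This is a safety-instruction inconsistency; it does not touch the primary endpoint, its analysis or the sample size. The conclusion rests on the current protocol text and assumes that the SPM does not already reconcile the sections.

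**What to change.** 1. **Restart rule.** Make Section 8.3.11.5 match Section 7.1.4, or replace its restart sentence with a pointer there. State in both sections that after QTc prolongation RPV or RPV LA may be restarted or continued only once the TdP drug is stopped and the Medical Monitor agrees.
2. **Scope of the bar.** State when the Section 7.1.4 sentence applies, so that it and Section 6.11 give one rule. Either option would do, and the choice is the sponsor's:
   - limit it to participants after QT prolongation, keep caution in Section 6.11, and add Medical Monitor contact before the next RPV dose; or
   - apply it generally, change Section 6.11 to match, and list TdP drugs in Section 6.11.1 under drugs taken with RPV.

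The cost is wording in two to four sections, with no added visits or tests. Some participants may have to switch the concomitant drug or wait for Medical Monitor review before the next RPV dose. The general bar costs more. Where the drug cannot be stopped, interrupting injections carries the resistance risk described in Section 6.9.1 and needs alternative antiretroviral cover. Before choosing it, the sponsor should check the SPM list against the alternatives that Section 6.11 itself suggests, such as azithromycin.
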